- Fatal or symptomatic bleed into a critical area or organ
- Bleeding leading to hospitalization
- Transfusion of 2 units or more packed red blood cells

Serious

- Bleeding leading to ED or UC visit or additional testing

After a major bleed, the participant will be removed from the extended follow-up interval and will not be eligible to qualify for the extended follow-up interval for 6 months after the event. After a serious bleed, the patient will be managed with usual care. If they did not have a permanent weekly dose change or if the temporary dose change was less than or equal to one month in duration, they must have 2 therapeutic INRs 4 weeks apart to begin the extended INR interval protocol.

If at any time a participant reports or clinic staff are alerted to a thromboembolic event, it will be documented in the EMR. The participant will be removed from the extended follow-up interval and not be eligible to qualify for the extended follow-up interval for 6 months after the event.

If at any time, anticoagulation clinic study staff do not feel it is appropriate to continue a participant with an extended follow-up interval, the participant can return to usual care. If at any time, the participant does not want to continue with an extended follow-up interval, they can return to usual care.

A participant will no longer be eligible for an extended INR interval if they meet any of the exclusion criteria at any time during the study, except for a bleeding or thromboembolic event. If a major bleeding or thromboembolic event occurs, they will be eligible to requalify after being on a stable warfarin dose for 6 months. A patient will also no longer be eligible for the extended INR interval if their INR goal changes and is no longer 2-3. A participant will be withdrawn from the study and no more data collected from the participant if they withdrawal their consent for the study or if death occurs.

A data monitoring committee will review the data collected, including bleeding and thromboembolic events for safety, protocol violations, and feasibility data at six months after the last patient is enrolled (at 3 months or when the 75th patient is enrolled), and then annually. If the data monitoring committee feels that the study is safe to continue, the study will continue until patients have been enrolled in the study for 2 years.

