The events rates for 2013 clinic data are listed below, including a 95%CI. Additionally, ranges for event rates over the past 4 years are included.

- Major bleed: 1.88% (95%CI 1.3-2.62%); range of 1.8-2%
- Serious bleed: 0.5% (95%CI 0.23-0.94%); range of 0-0.5%
- Thromboembolism: 0.22% (95%CI 0.06-0.6%); range of 0.2-0.44%

Stoppage rules for the study:

1. Stoppage rules for the study (based on event rates from the Schulman, et al. article) are included below. If the study is stopped early, all subjects will be scheduled for an INR within 6 weeks of their last INR, which is usual practice for the clinic.

Data from Schluman study				Madison VA	
Event	# from Schulman study	Rate per 1 year	95%CI of the 1 year rate from Schulman	Approx Count Based on 50 patients enrolled using upper end of 95% CI	Stoppage of Study
TE (includes TE-related death)	4	1.6%	0.4-4	2	3
Composite of TE, TIA, and major bleeding, TE-related death	12	4.8%	2.5-8.2	4.1	5

2. If an event occurs:
 - a. The PI or one of the Co-PIs will thoroughly evaluate the event to determine if it was related to study participation. . The following chart will be used to determine if the event was related to study participation.

Bleeding or TE event [‡]	On Extended Interval at Time of Event or within 6 Weeks of Event	INR Measure at visit following extended interval and/OR at Time of Event	Relationship to Hemostasis (as relates to INR direction/ magnitude)	Level of Attribution
Yes	Yes	Within target range	-	Possible
Yes	Yes	Outside target range	No relationship or uncertainty	Possible
Yes	Yes	Outside target range	Possible relationship	Probable
Yes	Yes	Outside target range	Definite relationship	Definite*

*Stopping rules apply to the events with a definite attribution. (Additional events may apply based on the discretion of the DMC and IRB.)

[‡] If the event was due to accident, injury, or other clear cause, attribution may not follow table.

- b. If a patient has a major bleeding or thromboembolic event, our protocol states that the patient will return to usual care and must be on the same dose for 6 months until they are able to requalify for the extended INR interval.

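### The stop counts (3 thromboembolic, 5 composite) are derived for 50 patients at one-year rates with no attribution filter shown, but applied by default to definite events over up to 150 patient-years

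*Combined protocol and SAP*

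**What the plan says.** All of this stands in the combined protocol and SAP, mostly under Procedures, Safety.

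- **Derivation.** The stoppage table takes one-year rates and 95% limits from the cited randomized trial of 4- versus 12-week assessment: TE 1.6% (0.4 to 4), composite 4.8% (2.5 to 8.2). Its derivation column is headed "Approx Count Based on 50 patients enrolled using upper end of 95% CI" and shows 2 and 4.1. The stops are 3 and 5.
- **Grading.** Item 2a states: "The PI or one of the Co-PIs will thoroughly evaluate the event to determine if it was related to study participation". The chart grades an event as definite only if the participant was on, or recently on, the extended interval, the INR was out of range, and the relationship to hemostasis was definite. Other charted events are possible or probable.
- **What counts.** The footnote reads "Stopping rules apply to the events with a definite attribution", followed by "Additional events may apply based on the discretion of the DMC and IRB". No criterion is given for adding events.
- **Exposure.** Enrolment is planned at 75 (Participants), or fewer if 3 months elapse first (Patient identification). If the DMC is content, "the study will continue until patients have been enrolled in the study for 2 years". The DMC meets "six months after the last patient is enrolled (at 3 months or when the 75th patient is enrolled), and then annually".
- **Clinic rates.** Listed just above the rules: "Major bleed: 1.88% (95%CI 1.3-2.62%); range of 1.8-2" and "Thromboembolism: 0.22% (95%CI 0.06-0.6%); range of 0.2-0.44" (both percentages).

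Nothing rescales the counts from 50 patients, gives them a time window, or explains the choice of 50.

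**The concern.** A stop count means something only relative to the events it counts and the exposure over which they accrue. Here both change between derivation and use. Restricting the tally to definite events makes 3 and 5 harder to reach than the table implies. Letting the tally run over up to three times the exposure makes them easier to reach.

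This is the only numeric study-level stopping criterion in the plan. As written, the DMC cannot tell how often it would be met at an acceptable or an unacceptable event rate, and that chance drifts as exposure accumulates. The rule could stop a study whose events match the cited trial's, or stay silent at the rates it was built to catch, depending on a share that the plan does not state.

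**Working it through.** **Reproducing the table.** 50 × 4% = 2.0 and 50 × 8.2% = 4.1. The first whole numbers above these are 3 and 5, as printed. The listed 4 and 12 events both imply a denominator of 250 (4/0.016; 12/0.048). Exact binomial limits for 4/250 and 12/250 are 0.44–4.05% and 2.50–8.23%, which match the table. This confirms the arithmetic. It does not show whether the source trial's events had been filtered by attribution.

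**Exposure.** Derivation: 50 patients × 1 year = 50 patient-years (PY). Plan: 75 × 2 = 150 PY at most, or 50 × 2 = 100 PY if only 50 enrol. On the table's own arithmetic with all events counted, 150 PY would give 150 × 4% = 6.0 TE and 150 × 8.2% = 12.3 composite events, not 2.0 and 4.1. These are expected counts, not proposed boundaries.

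**Chance of reaching the counts.** Let f be the share of events graded definite (not in the documents, so assumed and varied). Treat the counted events as Poisson with mean m = PY × rate × f. Then P(TE stop) = P(X ≥ 3) and P(composite stop) = P(X ≥ 5). Full enrolment, no dropout and all time on the extended interval are assumed.

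| Rates (TE / composite) | PY | f | m (TE / composite) | P(stop) TE / composite |
|---|---|---|---|---|
| Upper limits, 4% / 8.2% | 50 | 100% | 2.0 / 4.1 | 32% / 39% |
| Upper limits | 50 | 50% | 1.0 / 2.05 | 8.0% / 5.7% |
| Upper limits | 150 | 100% | 6.0 / 12.3 | 94% / 99% |
| Upper limits | 150 | 50% | 3.0 / 6.15 | 58% / 73% |
| Upper limits | 150 | 25% | 1.5 / 3.075 | 19% / 20% |
| Upper limits | 150 | 10% | 0.6 / 1.23 | 2.3% / 0.9% |
| Cited trial, 1.6% / 4.8% | 50 | 100% | 0.8 / 2.4 | 4.7% / 9.6% |
| Cited trial | 150 | 100% | 2.4 / 7.2 | 43% / 84% |
| Cited trial | 150 | 50% | 1.2 / 3.6 | 12% / 29% |
| Clinic, 0.22% / 2.10% | 150 | 100% | 0.33 / 3.15 | 0.5% / 21% |
| Clinic | 150 | 50% | 0.165 / 1.575 | 0.07% / 2.2% |

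The clinic rates are assumed to be annual. The clinic composite is 1.88% + 0.22% = 2.10%; TIA is not listed separately.

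**Where the mismatches cancel.** Setting PY × f = 50 gives f = 50/PY:
- 50 PY: 100%, so any filter makes the rule laxer than derived. With even accrual over 3 months, the first DMC review falls near this point: 75 × (0.75 − 0.125) = 46.9 PY.
- 100 PY: 50%.
- 150 PY: 33%.

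The 33% is a lower bound. The chart looks for time on the extended interval, and participants can leave it for months. If f is read as the share among events in on-interval time, and 70% of time is on-interval (assumed), then f = 50/(150 × 0.7) = 48%. At 50% of time on-interval it is 50/75 = 67%.

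**The case against.** Several points on the other side have force.

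- **The definite-only filter is a default, not an absolute.** The DMC and IRB may count further events. This stands, but with no criterion the clause does not calibrate the counts.
- **75 patients and 2 years are maximums.** Enrolment may fall short, participants spend time off the extended interval, and the two-year window is inferred from the study's duration. This also stands, and it is why the 33% is only a lower bound. But even 50 patients for 2 years gives twice the derivation's exposure, and the difference in event class remains.
- **Other protections exist.** Participants leave the extended interval after a TE or major bleed, and the DMC reviews bleeding and TE events and judges whether to continue. These limit the harm, but neither sets a study-level count.
- **This is a feasibility study without a powered test.** True, but safety is one of its three aims and the plan chose to set a numeric rule.

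A reader might infer that the rule is too lax, because it counts only definite events graded by the PI or a Co-PI, or too strict, because all-event counting at the cited trial's own rates would give 43%/84% by 150 PY. The documents support neither. Each reading takes one mismatch and ignores the other, and f is not given. Nor do they show that participants lack protection, or that the source trial's events were unfiltered; they show only that the table displays no filter.

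**Conclusion.** The point holds as a mismatch of basis. Counts derived for 50 patient-years with no attribution filter shown are applied by default to definite events over an exposure of up to 150 patient-years. Nothing in the plan connects the two.

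No direction of error can be assigned. At the table's upper limits, the rule at full exposure could be met almost always or almost never as f goes from 100% to 10%. It returns to its derived behaviour only at one value of f, and that value moves as exposure builds. The documentary mismatch needs no assumption. The percentages rest on Poisson counts, full enrolment, no dropout, full on-interval time and an assumed f, so they illustrate the spread and do not predict what this study would see.

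It should be fixed: it concerns a decision threshold, and the repair is cheap. The other safeguards keep it from being more serious.

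**What to change.** Reconcile the stoppage table and the footnote so that the counts are derived from, and applied to, the same event class, the same patient number and the same time window or accrued exposure. There are two ways:

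1. Count all qualifying events against counts scaled to exposure, and give the DMC the attribution chart as supporting information.
2. Keep definite-only counting, state the assumed definite share with its source and a range, and re-derive the counts under it.

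Either way, report the chance of crossing at the cited trial's rates and at the clinic's own rates. Whether the tally runs continuously or is assessed at DMC reviews, and where the boundary lies, are for the study team and the DMC; none is proposed here.

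The cost is a short amendment to one table and one footnote. No new data are needed: the events are already recorded, and time outside the extended interval is already a feasibility measure. The downside of the first route is possibly more boundary-triggered reviews. The downside of the second is a definite share that may be hard to source.

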2. To assess the safety of extending the interval of INR follow-up in patients.

Hypothesis: We hypothesize that there will not be a difference between the bleeding and thromboembolic events from baseline (12 months prior to study enrollment) to events/year at 6, 12, and 24 months.

Hypothesis: We hypothesize that there will not be a difference in the patient's time in therapeutic range (TTR) from baseline (12 months prior to study enrollment) compared to the TTR at 12 and 24 months.

3. To examine patients' and providers' acceptance of the intervention (to extend the follow-up interval of INR monitoring).

Hypothesis: We hypothesize that both patients and providers will favorably view the intervention.

Background:

Anticoagulation treatment with vitamin K antagonists, such as warfarin, can be complicated by many variables, such as drug interactions, diet, health status, other medications, and adherence. Frequent INR monitoring is required to keep patients' INR values within their target therapeutic range to lower the risk of hemorrhagic or thrombotic adverse events. However, some patients remain on the same warfarin dose with INRs within their goal range for extended periods of time. Predictors of very stable INR control for patients on long-term anticoagulation with warfarin include age greater than 70 years, male gender, INR target less than 3.0, and absence of heart failure, diabetes, or other chronic diseases.^{1, 2}

The most recent American College of Chest Physicians 2012 guidelines recommend an INR testing frequency of up to 12 weeks over 4 weeks in patients on warfarin with consistently stable INRs (Grade 2B; weak recommendation, moderate-quality evidence).³ The guidelines define stable INRs as at least 3 months of INRs that are within therapeutic range, thus not requiring changes in warfarin dose. These guidelines are now more comparable to those from the United Kingdom, where the practice of a 12-week INR monitoring interval has been usual practice.⁴ Despite the guideline recommendations, many United States anticoagulation providers are hesitant to extend the duration of INR follow-up to 12 weeks, as historically, the recommended interval and standard clinical practice for INR follow-up was a maximum of 4-6 weeks.

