within goal INR range for 6 or 12 months, to other patients, defined as one or more INRs outside of goal range during a 6 or 12 month period.^{1,2} Both studies found that bleeding and thromboembolic events were significantly lower with stable patients compared to the other patients on warfarin. Schulman et al. found no difference between the 4-week and 12-week groups in regards to major bleeding events, objectively verified thromboembolic events, and death.¹⁰ Schulman defined bleeding events per previously published criteria.¹¹ Although the Schulman et al study demonstrated favorable results, it is unknown if the patient contact every 4 weeks contributed to the positive outcomes. Additionally, the anticoagulation population in a VA Anticoagulation Clinic may be different (increased age, more comorbidities). Thus, we propose to examine an extended interval of INR follow-up in eligible patients at the William S. Middleton Memorial Veterans Hospital.

The Anticoagulation Clinic at the William S. Middleton Memorial Veterans Hospital and its associated community-based outpatient clinics is a pharmacist-managed service. The clinic currently follows approximately 1800 unique patients. The clinic manages the initiation of antithrombotic therapy, follows patients on short-term and long-term antithrombotic therapy, manages the transition from inpatient to outpatient care, and coordinates warfarin interruptions for procedures using low-molecular weight heparin if warranted. During an initial visit to the clinic, patients are oriented to warfarin as well as clinic procedures. A patient and provider responsibilities document is reviewed with all patients. For subsequent visits and INR assessments, patients are either seen in clinic or receive follow-up by telephone. The maximum interval between INRs is currently 5-6 weeks. Pharmacists have prescriptive authority under a scope of practice. This type of clinic is similar to other anticoagulation clinics in the Veteran Affairs system nationally and is considered high-quality anticoagulation management.¹²

Methods and Procedures

Design:

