Follow-up visits will be scheduled following the extended interval protocol, which includes visits at 5-6 weeks (if not already), then 7-8 weeks follow up, and then follow up at 11-12 weeks, if the participant continues to be on a stable dose of warfarin and the INRs are within the goal range of 2-3 (including lab variation) (figure 1). If the participant is already at a 5-6 week follow-up, which is usual care, their next follow-up interval will be 7-8 weeks. Follow-up visits will continue to be scheduled at 11-12 weeks if those criteria are met. If a situation arises where the extended interval is no longer appropriate (e.g. single INR outside of goal range and lab variation, a participant has a procedure requiring interruption of warfarin, drug interaction, hospitalization, etc.), the clinical situation will be managed per usual care (figure 2). If there was a permanent weekly dose adjustment or if the temporary dose change was more than 1 month, the participant would return to usual clinic care. They could requalify for the extended interval protocol when they have been on the same warfarin dose for at least 6 months, except for a single, one-time adjustment. Planned procedures with INR(s) out of range would not exclude a patient. If there was not a permanent weekly dose adjustment or if the temporary

dose change was less than or equal to one month, two therapeutic INRs 4 weeks apart will be needed prior to starting the participant on the extended interval.

If an unexpected INR is drawn, the pharmacist provider will assess the reason why the INR was drawn (figure 3). If it was due to a change in health status, the participant would most likely require shorter follow-up which would meet the criteria for the situation described previously. If it was truly a random INR, the next follow-up should be scheduled for the originally intended interval (e.g. Scheduled for 8 week follow-up and INR was drawn at 6 weeks. Next follow-up scheduled for 8 weeks).

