Patient satisfaction: Study participants will receive a survey at baseline and at approximately 6, 12, and 24 months. The survey includes the Duke Anticoagulation Satisfaction Scale, a validated survey instrument assessing a participant's satisfaction with their anticoagulation therapy and management.¹³ If the participant has a face-to-face visit, they will fill out a paper copy of this survey during a clinic visit. If the participant has a telephone visit, the survey will be mentioned during the phone call and the participant will be mailed a copy of the survey with a pre-addressed stamped envelope. If the participant has a secure messaging visit, the survey will be mentioned in the return secure message and the participant will be mailed a copy of the survey with a pre-addressed stamped envelope. If the survey is not received by study staff within 2 weeks of the visit, the participant will be called to remind them to mail in the survey. Participants will be called up to three times to remind them to mail in the survey. At the end of the study, 10 randomly chosen participants will be asked if they would be interested in attending a focus group to explore their opinions further.

Provider satisfaction, confidence, and knowledge: Pharmacist providers who are study team members will be surveyed prior to the enrollment of the first participant about their knowledge of and confidence with the extended interval protocol. At the end of the study, all pharmacist

providers who are study staff will be invited to attend a focus group to discuss the feasibility of incorporating extended INR intervals into the anticoagulation clinic as well as their satisfaction and attitudes.

Quality assurance: A member of the study staff not involved with the participant's direct warfarin management will conduct a chart review. The chart review will be conducted to evaluate inadvertent protocol violations by anticoagulation study staff in the management of the study participants. Deviations will be categorized and quantified by type and frequency of protocol violation.

Safety: If at any time a participant reports or clinic staff are alerted to a bleeding event, it will be documented in the participant chart, as per standard of care practice. The following criteria, which are currently used in the Anticoagulation Clinic at the Madison VA to collect bleeding and thromboembolic events, will be used to differentiate major and serious bleeding:

Major

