Adverse events (AEs) collected for this study only include bleeding and thromboembolic events. Serious adverse events (SAEs) will be documented per VA and IRB definitions. AEs will be entered into OnCore after the retrospective review of the medical record at 6, 12, and 24 months after participant enrollment in the study. SAEs are entered into the SAE documentation area in OnCore as they occur, which may not align with the time period for the chart review. The SAEs that include bleeding or thromboembolism will be entered in real-time to the AE table in OnCore.

Measures: The outcomes of this study include feasibility, safety, and acceptability of extending the interval of INR follow-up to 12 weeks in stable warfarin patients. We propose to use the following measures:

1. Feasibility: We will examine the following:
 - a. Rates of participant accrual (patient interest in participating and reasons for not participating). Number of withdrawals and reasons for withdrawal from protocol or study.
 - b. Change in frequency of appointments from baseline
 - c. Frequency and type of protocol deviations from both participants and study staff
 - d. Frequency of time outside of extended INR interval protocol and why
 - e. Knowledge assessment of study staff regarding study protocol
2. Safety: We will examine the following:
 - a. Participant reported and EMR review of bleeding events. Study participant bleeding events for 12 months prior to enrollment and during the study will be compared to the clinic's bleeding event rate. The following definitions will be used to categorize bleeding:
 - i. Major
 1. Fatal or symptomatic bleed into a critical area or organ
 2. Bleeding leading to hospitalization
 3. Transfusion of 2 units or more PRBCs
 - ii. Serious
 1. Bleeding leading to ED or UC visit or additional testing
 - b. Participant reported and EMR review of thromboembolic events that are objectively verified. Study participant thromboembolic events for 12 months prior to study enrollment and during the study will be compared to the clinic's thromboembolic event rate.
 - c. Participant reported and EMR review of healthcare utilization: hospitalizations, ED visits, urgent office visits, telephone triage related to anticoagulation. Utilization for 12 months prior to study enrollment will be compared to utilization during study enrollment.
 - d. Baseline TTR (12 months prior and 6 months prior) for each patient and during study¹⁴
 - e. Number of extreme INRs (<1.5, ≥4.5)

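### Events known only from participant report are prompted about half as often on the full extended interval as under usual care, so they may be captured later or less completely on study; event source should be recorded and a fixed-time event question added

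*Combined protocol and SAP*

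**What the plan says.** Measures, item 2 (Safety) names the same two sources for each outcome. The bleeding item begins "Participant reported and EMR review of bleeding events. Study participant bleeding events for 12 months prior to enrollment and during the study"; the item on clots has "Participant reported and EMR review of thromboembolic events that are objectively verified"; utilization is put in similar terms. For bleeds and thromboembolism that section names the clinic's own event rate as comparator, covering both the prior 12 months and the study period. For utilization it compares the prior 12 months with the study. The baseline-to-study comparison of bleeds and thromboembolism is in Specific Aims, Aim 2, whose hypothesis reads "there will not be a difference between the bleeding and thromboembolic events from baseline (12 months prior to study enrollment) to events/year at 6, 12," with month 24 as the last time point.

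Procedures, Intervention places the routine enquiry about health changes at the assessment that follows each INR. Procedures, Safety adds an unscheduled route: "If at any time a participant reports or clinic staff are alerted to a bleeding event", it is charted.

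On timing, Background says of usual care: "The maximum interval between INRs is currently 5-6 weeks". On study the interval goes to 7-8 and then 11-12 weeks, and "Follow-up visits will continue to be scheduled at 11-12 weeks if those criteria are met". The text before Measures states that "AEs will be entered into OnCore after the retrospective review of the medical record at 6, 12, and 24 months after participant enrollment"; serious adverse events that are bleeds or thromboembolism are entered in real time.

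Patient satisfaction describes surveys at baseline and about 6, 12 and 24 months that include a satisfaction scale. No event question is described. Analysis names McNemar, paired t and Wilcoxon tests, with no breakdown by event source.

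**The concern.** The intervention alters the schedule on which one of the two event sources is collected. A bleed treated at a non-VA hospital reaches the VA record only if somebody tells the clinic, and the routine occasion for telling it is the post-INR assessment. EMR review does not wholly remove the dependence, because bleeds that participants report are themselves charted: part of the record is a product of contacts.

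The baseline year was lived under visits at most 5-6 weeks apart, and the clinic rates come from a clinic with the same maximum. A lower or later yield of report-only events on study pulls the study count down against both comparators. A true rise could be partly hidden. If nothing had changed, the same effect would appear as a small false fall. The protocol says its results may inform larger studies, so an unlabelled ascertainment difference could carry forward.

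**Working it through.** The documents give no figure for event capture, so there is none to reproduce.

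**Step 1: prompts per year.** Inputs are the intervals in Background and Procedures, Intervention. Contacts per year = 52 / interval in weeks.
- Usual care: 52/6 = 8.7 to 52/5 = 10.4.
- Full extended interval: 52/12 = 4.3 to 52/11 = 4.7.
- Ratio at mid-intervals: r = 5.5/11.5 = 0.48 (range 5/12 = 0.42 to 6/11 = 0.55).

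Counting the step-up, an on-schedule participant has 4-5 scheduled visits in year 1, against 8-10 under usual care.

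**Step 2: the cohort.** If a share f of study time is on the full interval and the rest is at the usual frequency, the ratio is f × 0.478 + (1 − f). For f = 75%, 50% and 25% this gives 0.61, 0.74 and 0.87. The documents do not give f.

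**Step 3: effect on counts.** Let q be the share of qualifying events known only by report (assumed; not in the documents). In the worst case report capture is proportional to contacts, and observed/true = 1 − q(1 − r). Expected events in 75 patients at the 2013 clinic rates are 75 × (1.88% + 0.5% + 0.22%) = 1.95 a year.

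| q | observed/true | events lost per year |
|---|---|---|
| 0% | 1.00 | 0 |
| 5% | 0.97 | 0.05 |
| 10% | 0.95 | 0.10 |
| 25% | 0.87 | 0.25 |
| 50% | 0.74 | 0.51 |

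If an event is simply mentioned at the next, later visit, the eventual loss is near zero. An intermediate case is recall that decays with an assumed half-life of 12-52 weeks. Capture over an interval L is then c(L) = (1 − exp(−kL))/(kL), with k = ln 2 / half-life. The shortfall is 1 − [(1 − q) + q·c(11.5)] / [(1 − q) + q·c(5.5)], which is 0.9-6.8% for q of 25-50%.

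**Step 4: time not yet asked about at each review.** Study reviews are dated from enrolment, not from a contact. With on-schedule visits drawn uniformly within 5-6, 7-8 and repeated 11-12 weeks, the mean time since the last visit is:

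| Entry step | 26 weeks | 52 weeks | 104 weeks |
|---|---|---|---|
| 7-8 weeks | 7.0 (27%) | 9.9 (19%) | 4.5 (4%) |
| 5-6 weeks | 1.5 (6%) | 4.5 (9%) | 8.9 (9%) |

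Only report-only events in that time are exposed, and those missed at 6 or 12 months can be found at a later review.

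**Step 5: the opposing bias.** Participants exclude patients with a medically treated bleed or clot in the past 6 months. If this removes about half of the baseline year's events (uniform rate assumed), the study/baseline ratio with no true change is 1/0.5 = 2.0 at q = 0 and 0.739/0.5 = 1.48 at q = 50%. Capture loss would cancel the exclusion only at q = 0.5/(1 − 0.478) = 96%.

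**Step 6: chance.** Major bleeds and thromboembolism over 150 patient-years: 150 × (1.88% + 0.22%) = 3.2 expected. Exact McNemar power with 75 patients (two-sided 0.05 and independent periods assumed) for a true 2-, 3- or 4-fold rise in the three event types combined is 4%, 17% and 36% with full capture. With capture of 0.87 it is 3%, 11% and 26%.

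**The case against.** The strongest reply is that most qualifying events leave a record whatever the visit interval. Major and serious bleeds are largely defined by hospitalization, transfusion, an emergency or urgent-care visit, or testing; thromboembolism must be objectively verified; records are reviewed at fixed times; and real-time entry of serious events is an on-study addition. Baseline data are listed as coming from the medical record, so net capture could even rise on study. This stands as a limit on size. It does not cover encounters outside the VA that nobody reports, and real-time entry also requires staff to know of the event.

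Three stronger readings are tempting, and the documents do not support them. First, a reader might infer that capture falls by construction. Only report-only events are exposed, their share is not given, and a longer interval may delay a report rather than lose it. Second, a reader might infer that the bias favours a finding of no difference. For bleeds and thromboembolism against baseline, the six-month exclusion pushes the other way, probably harder (Step 5); a null result would be likely mainly because of the sample size (Step 6). Third, a reader might take the 27% tail as the typical loss. It is the 6-month value for one entry group. Nothing says that an event reported after a cut-off is discarded, and the surveys are themselves tied to visits with reminder calls. The first data monitoring review comes six months after the last enrolment, when earlier enrollees are past that point.

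It is also fair that the survey instrument is not in the documents, so an event question cannot be ruled out; none is described.

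**Conclusion.** The point holds in a limited form. Participant report is one of two event sources, its planned prompt is tied to INR visits, and those prompts roughly halve for a participant on the full extended interval. The plan describes neither a fixed-time event question nor an analysis by source. Report-only events may therefore be captured later or less completely on study, which can mask a rise.

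The size cannot be determined. In the worst case, at an assumed report-only share of 25-50%, the count is 13-26% low, or 0.25-0.51 events a year in 75 patients at clinic rates; under simple delay it is near zero. For major bleeds and thromboembolism this is small against chance, and a net bias toward no difference is not shown. The concern is least opposed for utilization, which the exclusion does not cover in general, and for the clinic-rate comparison, where the emptied half of the baseline year plays no part in the on-study contrast. These figures assume that clinic rates apply to this stable cohort and that participants stay on schedule. It is a cheap improvement, not a flaw that defeats the study.

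**What to change.** 1. Keep the 6-, 12- and 24-month windows. Assign each event to a window by its date of occurrence, and update that window's count after the first clinic contact following the cut-off. Data monitoring reviews and real-time entry of serious events should not wait for this.
2. Add a short fixed block to the existing 6-, 12- and 24-month surveys: any bleed, clot, or emergency, urgent-care or hospital visit since the last survey, with date and place. Verify positive answers in records. If a baseline version is used, state that its 12-month recall is not equivalent to the on-study recall.
3. Record the source of each event as a health-care encounter record or participant report only, the latter including reports charted by the clinic. Repeat the baseline-to-study and clinic-rate comparisons with encounter-record events only as a sensitivity analysis; for the clinic rate, only if its source data allow the split.

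The cost is a few more survey items, imprecise recall, and slightly later final counts for some participants. No clinical management changes.
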